AE: adverse event; ctDNA: circulating tumor DNA; ECG: electrocardiogram; ECOG: Eastern Cooperative Oncology Group; ELISpot: enzyme-linked immunospot; EOT: end of treatment; iCPD: “immune” confirmed progressive disease; iUPD: unconfirmed disease progression disease based on iRECIST; SAE: serious adverse event; WOCBP: woman of childbearing potential; WT1: Wilms’ tumor 1 protein.

Footnotes continued on next page

- a. For participants in ASP7517 monotherapy treatment arm. Participants in the Observation period will be followed until iCPD, iUPD who are not clinically stable, clinical disease progression, initiation of a new anticancer therapy or for a total of up to 48 weeks starting at EOT, whichever occurs first.
- b. Maximum of 8 samples collected during the Observation Period. Sample will be collected at the time of the disease assessment visit.
- c. Maximum of 4 samples collected during the Observation Period. Sample will be collected at the time of the disease assessment visit.
- d. Sample will be collected only at the time of discontinuation due to disease progression.
- e. Outcomes will be assessed by telephone calls every 3 months for up to 12 months.
- f. In Monotherapy Arm, Safety Follow-up is a part of 48 weeks of Observation period. Observation period starts after EOT.

Table 4 Schedule of Assessments for Observation Period, Safety Follow-up and Survival Follow-up for Participants who Receive Pembrolizumab Monotherapy in the Observation Period

Visit	Observation Period Up to 96 weeks ^a	Safety Follow-up			Survival Follow-up
	Visits every 6 weeks (\pm 1 week) from last Pembrolizumab dose during combination treatment	30 days from last dose	60 days from last dose	90 days from last dose	Every 3 months
Window (days)		\pm 3	\pm 3	\pm 3	\pm 7
Physical Examination	X	X	X	X	
Vital Signs	X ^b	X	X	X	
ECOG Performance		X	X	X	
Concomitant Medications	X	X	X	X	
12-Lead ECG	X ^c	X	X	X	
Clinical Laboratory Tests (chemistry, hematology, coagulation, urinalysis)	X ^c	X	X	X	
Thyroid Profile Panel (triiodothyronine or free triiodothyronine, free thyroxine and thyroid stimulating hormone)	X ^c	X ^c			
Pregnancy Test for WOCBP	X ^c	X	X	X	
AE/SAE Assessment	X	X	X	X	
Pharmacokinetic samples for cell kinetics (ASP7517)	See Table 6 for schedule				
Pharmacokinetic sample for pembrolizumab	See Table 6 for schedule				
Blood Sample for anti-WT1 antibody	X ^{c,h}				
Blood Sample for Immune Response Biomarker (ELISpot)	X ^{c,g}				

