Blood Sample for Immune Response Biomarker (Tetramer)	X ^{c,h}				
Blood Sample for Immune Cell Phenotyping	X ^{c,g}				
Blood Sample for Cytokines	X ^{c,g}				
Blood Sample for ctDNA	X ^{c,f}				
Radiographic Disease Assessment	X ^d				
Pembrolizumab Dosing	X ^e				
Survival Follow-up ⁱ					X

AE: adverse event; C5D15: Cycle 5 Day 15; CR: complete response; ctDNA: circulating tumor DNA; ECG: electrocardiogram; ECOG: Eastern Cooperative Oncology Group; ELISpot: enzyme-linked immunospot; iCPD: “immune” confirmed progressive disease; iUPD: unconfirmed disease progression disease based on iRECIST; PR: partial response; SAE: serious adverse event; SD: stable disease; WOCBP: woman of childbearing potential; WT1: Wilms’ tumor 1 protein.

Footnotes continued on next page

- a. For participants in ASP7517 and pembrolizumab treatment who have achieved CR, PR or SD and receiving pembrolizumab monotherapy. Pembrolizumab will be administered every 6 weeks for up to a total of 17 doses. Participants in the Observation period will be followed until iCPD, iUPD who are not clinically stable, clinical disease progression, initiation of a new anticancer therapy or for a total of up to 96 weeks, whichever occurs first. If participant discontinues pembrolizumab at any time during the 78-week Observation period, the participant will continue with Safety Follow-up visits, then resume Observation period visits every 6 weeks until iCPD, iUPD who are not clinically stable, clinical disease progression, initiation of a new anticancer therapy or for a total of up to 78 weeks from last dose of ASP7517, whichever occurs first. If participant discontinues combination treatment of ASP7517 at any time prior to C5D15, then the participant should continue observation period up to 96 weeks.
- b. Vital signs should be obtained prior to pembrolizumab infusion and within 30 min (\pm 10 min window) after completion of pembrolizumab infusion.
- c. Obtained predose.
- d. Disease assessment every 8 weeks.
- e. Pembrolizumab administered every 6 weeks for up to 17 doses total (for the study) for those participants who, in the opinion of the investigator, are continuing to derive clinical benefit.
- f. Sample collected at the time of discontinuation due to disease progression.
- g. Sample collected at the time of pembrolizumab administration of doses 5 and 7 (i.e., 2 samples are collected from the time the participant enters the Observation Period).

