	15	Predose	- 60 min ^a	X			
		End of pembrolizumab Infusion	+ 15 min ^c	X			
Cycle 6	1	Predose	- 60 min ^d		X		
		End of ASP7517 Infusion	+ 15 min ^c		X		
EOT	EOT	-	-	X	X	X	X
Safety Follow-up ^e	30 days	NA	-		X		
Observation Period Pembrolizumab Monotherapy: Doses 5 and 6 ^f	1	Predose	- 60 min ^a	X	X	X	
		End of pembrolizumab Infusion	+ 15 min ^b	X		X	

CR: complete response; EOT: end of treatment; NA: not applicable; PK: pharmacokinetics; .

- a. Within 60 min prior to pembrolizumab infusion.
- b. Within 15 min after the end of pembrolizumab infusion (before the infusion of ASP7517 on C1D1 and C4D1).
- c. Within 15 min after the end of ASP7517 infusion.
- d. Within 60 min prior to ASP7517 infusion.
- e. For participants in ASP7517 monotherapy arm and participants in ASP7517 and pembrolizumab combination therapy arm who end the treatment early or completed the treatment period [see [Table 3](#)].
- f. For participants in ASP7517 and pembrolizumab combination therapy arm who receive pembrolizumab monotherapy in the Observation Period [see [Table 4](#)]. Doses 5 and 6 are the first 2 doses of pembrolizumab in the Observation Period when 6 cycles in the Treatment Period are completed. If the Treatment Period ends earlier than Cycle 6 and pembrolizumab monotherapy continues in the Observation Period, pembrolizumab PK is continued to the 6th dose of pembrolizumab from C1D1.
- g. Sample not collected in Stage 2 of Dose Expansion.
- h. Pembrolizumab PK samples only applicable for participants in the combination therapy arm.

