4.1.1 Study Periods

For participants in all arms/phases, the study consists of the following periods:

- Screening: (up to 28 days)
- Treatment (up to six 28-day cycles):
 - ASP7517 Monotherapy Arm: ASP7517 every 28 days
 - ASP7517 and Pembrolizumab Combination Therapy Arm: ASP7517 every 28 days and pembrolizumab every 6 weeks in combination (up to 6 doses of ASP7517 in combination with up to 4 doses of pembrolizumab);
- End of Treatment (EOT) Visit: Participants will complete an EOT visit within 7 days of EOT determination or prior to initiation of new anticancer therapy

- Safety Follow-up: Participants will complete 30-day, 60-day and 90-day safety follow-up visits from the last dose of study drug or prior to the initiation of new anticancer therapy
- Observation Period:
 - Observation Period for Monotherapy: All participants will enter an observation period after EOT, except those with iCPD, iUPD (per independent central review or local review) and who are not clinically stable or clinical progression is confirmed by the investigator. The observation period consists of safety follow-up visits (30, 60 and 90 days after last dose administered in the treatment period) and visits for only tumor imaging (every 8 weeks for up to 48 weeks).
 - Observation Period for Combination Therapy: Participants will enter an observation period 6 weeks from the last dose of pembrolizumab in combination with ASP7517 (up to 96 weeks and may receive pembrolizumab monotherapy up to a total of 17 doses every 6 weeks for qualifying participants).
- Survival Follow-up: Telephone contact will be made every 3 months for up to 12 months.

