7.1 Efficacy Assessments

Disease response and progression will be evaluated in this study using the RECIST v1.1 and iRECIST criteria as assessed by independent central review and investigator.

Tumor assessments will be performed at screening and at every 8 weeks (\pm 1 week) from C1D1 until confirmed disease progression by iRECIST (iCPD). Scans will be read on site and also submitted in digital format for independent central review. Procedures for independent imaging central review will be described in a separate imaging charter. The assessment will include tumor measurements for target lesions, non-target lesions, and assessment for any new lesions. An overall assessment will be characterized for time point evaluation.

Computed tomography (CT) or magnetic resonance imaging (MRI) scans are preferred for this study and to ensure comparability, the same technique (CT/MRI) used at screening should be utilized throughout the study. The same method should be employed and assessed by the same individual on each occasion, when possible. Imaging should include chest, abdomen and pelvis as well as any other anatomical region appropriate for the participant's disease.

Imaging should be done every 8 weeks from C1D1 regardless of treatment interruption or delays and through the follow-up period as applicable. Scans performed prior to informed consent as standard of care are acceptable as screening scans if done within 28 days prior to C1D1. If a biopsy of a target lesion is performed, the baseline scan should be repeated, if possible.

Confirmatory scans for CR or PR should be done at least 4 weeks after the date of the scan that CR or PR was first observed. Confirmatory scans for PD must occur at least 4 weeks after the date of the scan that PD was first observed but no longer than 8 weeks.

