iUPD before new ACT and is in one of the following cases : a)if the participant stops protocol treatment because they were not judged to be clinically stable, b) no further response assessments are done (because of participant refusal, protocol non-compliance, or participant death); c) the next timepoint responses are all iUPD, and iCPD never occurs;	First date where iUPD criteria are met	Event
Missed ≥ 2 scheduled radiological assessments		
If last assessment prior to missing ≥ 2 scans is iUPD	First date where iUPD criteria are met	Event
If last assessment prior to missing ≥ 2 scans is not iUPD and no progression or death after missing ≥ 2 scans	Date of last radiological assessment	Censor

iPFS		
Situation	Date of Event or Censor	Outcome
No post-baseline tumor imaging prior to missing 2 scans and progression or death after missing ≥ 2 scans	Date of first dose (Day 1)	Censor
No post-baseline tumor imaging prior to missing 2 scans and no progression or death after missing ≥ 2 scans	Date of last radiological assessment	Censor
If radiographical progression or death occurs after missing 2 scheduled radiological assessments and last assessment prior to missing ≥ 2 scans is not iUPD	Date of last radiological assessment before missing 2 scans	Censor

iPFS = Date of Event or Censor – Date of First Dose +1

Missing 2 scheduled imaging assessments:

Missing 2 scheduled imaging assessments is defined as the gap between two imaging assessments being more than 140 days (2.5 times the scheduled imaging assessment interval (2.5 x 56 days)). Imaging assessments after first iUPD will be excluded from PFS derivation.

Note: Participant cannot be censored at “NE”. If NE is the only previous assessment, then iPFS will be censored at Day 1.

To apply the cut-off date to iPFS is to exclude those tumor assessments after cut-off date and anti-cancer therapy date after cut-off date in the analysis.

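### After pembrolizumab is stopped, protocol Table 4 schedules no scans during safety follow-up; this conflicts with Section 7.1 and can open a gap longer than the SAP's 140-day limit

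*Protocol*

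**What the plan says.** **Table 4 (protocol Section 1.3).** This schedule covers combination participants who receive pembrolizumab alone in the Observation Period. Its "Radiographic Disease Assessment" row is marked in the Observation column only, with footnote d: "Disease assessment every 8 weeks". The 30-, 60- and 90-day safety columns are blank in that row and stand outside the Observation heading. For a participant who stops pembrolizumab, footnote a says that "the participant will continue with Safety Follow-up visits, then resume Observation period visits every 6 weeks until iCPD". Section 4.1.1 counts the safety visits from the last dose: "Participants will complete 30-day, 60-day and 90-day safety follow-up visits from the last dose of study drug".

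**Section 7.1.** "Imaging should be done every 8 weeks from C1D1 regardless of treatment interruption or delays and through the follow-up period as applicable". The same section sets iCPD as the end of imaging.

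**Monotherapy (protocol Table 3, footnote f).** "In Monotherapy Arm, Safety Follow-up is a part of 48 weeks of Observation period". The safety columns there sit under the Observation heading.

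**SAP 5.1.2.5 and 5.1.2.6.** "Missing 2 scheduled imaging assessments is defined as the gap between two imaging assessments being more than 140 days". Progression or death after such a gap is censored at the last scan before it. For iPFS there is an exception: if that last scan was iUPD, an event is counted at the first iUPD date.

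**Length of the combination Observation Period.** Section 4.1.1 gives 96 weeks. Section 4.1.3 gives 78 weeks from EOT, or 96 if ASP7517 stops before C5D15. Table 4 footnote a gives 96 weeks, and also 78 weeks from the last ASP7517 dose. SAP Section 2.2 gives 78.

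**The concern.** Footnote a puts two periods in sequence, and the only period with a scan mark is the one that waits. Section 7 treats adherence to the schedule tables as mandatory, so a site has good reason to work from Table 4. Section 7.1 qualifies its follow-up clause with an applicability condition, so it does not clearly override the table. Two sites could follow the protocol in good faith and scan the same kind of participant differently.

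Those affected stop pembrolizumab without iCPD, clinical progression or new anticancer therapy. They are foreseeable, because Table 17 requires permanent discontinuation for several immune-related events. Their progression could be dated late. If the gap passes 140 days, the SAP would drop it as an event, although the gap came from the schedule and not from missed visits.

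**Working it through.** **The SAP's figure.** 2.5 × 56 = 140 days, as stated.

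**Section 7.1 followed.** Scans every 56 ± 7 days give a longest gap of 56 + 14 = 70 days. With one scan missed it is 112 + 14 = 126 days. Both are below 140, so the schedule alone never triggers censoring.

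**Table 4 followed literally.** Inputs are pembrolizumab every 42 days, scans every 56 days (Table 4) and the last safety visit on Day 90. Place dose k on day 42(k − 1) and scans on multiples of 56. From dose 5 onward, the lag from the latest scan to the dose cycles through 0, 42, 28 and 14 days. Let t be the days from last dose to the decision to stop, and R the day of the first resumed scan, counted from the last dose. Then

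gap = lag + R, less 56 if lag + t is 56 or more (one more scan was done before the stop).

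The documents do not fix R, so four restart dates are shown: (a) the Day-90 visit; (b) the next date on the 8-week scan grid; (c) the next date on the 6-week dosing calendar, 3 × 42 = Day 126; (d) six weeks after the Day-90 visit, Day 132. They do not give t either; it is first taken as uniform over 0 to 42 days.

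| Lag | t (days) | (a) | (b) | (c) | (d) |
|---|---|---|---|---|---|
| 0 | 0–42 | 90 | 112 | 126 | 132 |
| 42 | 0–14 | 132 | 168 | 168 | 174 |
| 42 | 14–42 | 76 | 112 | 112 | 118 |
| 28 | 0–28 | 118 | 168 | 154 | 160 |
| 28 | 28–42 | 62 | 112 | 98 | 104 |
| 14 | 0–42 | 104 | 112 | 140 | 146 |

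Share of stop times with a gap over 140 days, out of 4 × 42 = 168 lag-days:
- (a) none; the longest gap is 132 days.
- (b) (14 + 28)/168 = 25%.
- (c) (14 + 28)/168 = 25%; the 140-day gap is at the limit, not over it.
- (d) (14 + 28 + 42)/168 = 50%.

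Share with a gap over 70 days, the most that Section 7.1 allows: under (a), 1 − 14/168 = 92%; under (b) to (d), 100%.

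**Later decisions.** Table 17 allows up to 12 weeks (84 days) from the last dose before an unresolved event forces discontinuation. With t uniform over 0 to 84, no further gap exceeds 140 days and the denominator doubles to 336. The shares become 42/336 = 12.5% for (b) and (c), and 84/336 = 25% for (d).

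**Observation length.** Thirteen further doses take 13 × 6 = 78 weeks; the 16 intervals between 17 doses take 96 weeks. For participants who continue pembrolizumab, Table 1 footnote t and Table 2 footnote s place EOT after dose 17 or after the decision to stop. A 78-week period starting at EOT therefore cannot contain those doses.

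**The case against.** The strongest reply is that no sentence suspends imaging. Section 7.1 requires it regardless of treatment status. What footnote a resumes is the 6-weekly visit stream, while scans keep their own 8-week interval under footnote d. Blank cells prove little, since protocol Table 3 also leaves the scan row blank under its safety columns and monotherapy scans are still expected. A site following Section 7.1 never nears 140 days.

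Much of this stands. A reader might infer that the protocol halts scans and that censoring follows; the documents support only a conflict between two passages. The conflict is still real. Table 3's safety columns lie inside the Observation Period by heading and by footnote f. Table 4's do not, and its footnote puts the periods in sequence.

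Three other readings go too far:
- **A bias between arms.** No comparison of monotherapy with combination is planned. Each cohort has its own hypothesis (protocol 9.1), and SAP 6.1 calls for separate displays.
- **Inflated duration of response.** SAP 6.4.2.7 and 6.4.2.8 only list iDOR and DOR.
- **A further contradiction in Table 6 footnote e.** Its reference to "participants in ASP7517 and pembrolizumab combination therapy arm who end the treatment early or completed the treatment period" defines who gives a 30-day pharmacokinetic sample. It sets no observation length.

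**Conclusion.** The point holds as an inconsistency between Table 4 (footnote a and the scan row) and Section 7.1. Its practical effect depends on which passage a site follows. Under Section 7.1 there is none. Under Table 4 alone, late detection is nearly certain for those affected. Censoring ranges from 0% to about 50% of stop times, depending on the undefined restart date and on when the decision to stop is made. No single percentage can be drawn from the documents, and these rest on a nominal calendar without visit windows.

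The reach is limited. It concerns mainly PFS and iPFS in combination participants who stop pembrolizumab progression-free, and iPFS is protected when the last scan before the gap is iUPD. The study closed early (SAP 5.1.1), and the documents do not say how many participants were in this position. The differing observation lengths and starting points are a second inconsistency, which stands whichever passage governs imaging.

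**What to change.** In Table 4, state in footnotes a and d that imaging every 8 weeks from C1D1 continues in parallel with the safety follow-up visits, as Section 7.1 requires, and mark the scan row to match. Make the same change to the scan row of Table 22. Its footnote a lacks the sentence about resuming visits, so only the row needs it.

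Reconcile the length and starting point of the combination Observation Period across Sections 4.1.1 and 4.1.3, Table 4 footnote a and SAP Section 2.2.

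The cost is table and footnote wording. The scans restored are ones that Section 7.1 already requires. If the protocol is no longer being amended, the clinical study report can list any combination participant with a scan gap over 140 days after stopping pembrolizumab and show how PFS and iPFS were handled.

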2 INTRODUCTION

In this study (7517-CL-1101), ASP7517 is indicated as a single agent and in combination with pembrolizumab in participants with advanced solid tumors known to express the Wilms' tumor protein 1 (WT1) antigen.

Details about ASP7517 are provided in the Investigator's Brochure.

Details about pembrolizumab are provided in the summary of product characteristics/package insert of this product.

2.1 Study Rationale

Accumulating evidence indicates that the WT1 gene plays an oncogenic function in leukemogenesis and tumorigenesis. The WT1 gene is highly expressed in leukemia and various types of solid tumors (e.g., melanoma, ovarian cancer and colon cancer) and is listed at the top of the ranking of tumor antigen [Sugiyama, 2010]. In addition, WT1 tumor antigen expression plays an important role in the progression of disease and prognosis of human malignancies [Qi, 2015; Sugiyama, 2010]. ASP7517 has effects against WT1 expressing tumors by inducing both natural killer cell activity (innate immunity) and WT1-specific T cell dependent antitumor effects (adaptive immunity). Nonclinical studies were performed to demonstrate that both the innate and adaptive immune systems were activated by artificial Adjuvant Vector Cell (aAVC). In addition, nonclinical data suggest that ASP7517 is active in WT1 expressing tumor as described in Sections 4.1.1.2.5, 4.1.1.2.6 and 4.1.1.2.7 of the Investigator's Brochure; therefore, ASP7517 treatment for solid tumors known to express WT1 may result in clinical benefit.

2.2 Background

The WT1 gene was isolated as the gene responsible for a childhood renal neoplasm, Wilms' tumor, which was thought to arise as a result of inactivation of both alleles of the WT1 gene located at chromosome 11p13 [Gessler et al, 1990]. This gene encodes a zinc finger transcription factor that plays an important role in cell growth and differentiation [Sugiyama, 2001].

The WT1 gene is also expressed at high levels in almost all types of solid tumors, with its expression level serving as a significant prognostic factor. Cancers over-expressing WT1 include melanoma, leukemia, breast cancer, ovarian cancer, glioblastoma, soft tissue sarcoma and colorectal cancer (CRC) [Bejrananda et al, 2010; Wagner et al, 2008; Nakatsuka et al, 2006; Miyoshi et al, 2002; Menssen et al, 2000; Oji et al, 1999; Miwa et al, 1992].

In addition to its prognostic role in a variety of cancer types [Köbel et al, 2008; Sotobori et al, 2006], WT1 is recognized as a promising target for immunotherapy based on its unique features [Dao et al, 2013; Cheever et al, 2009]. In addition, WT1 tumor antigen expression plays an important role in the disease progression of human malignancies [Qi, 2015; Sugiyama, 2010].

ASP7517 has effects against WT1-expressing tumors by inducing both natural killer (NK) cell activity (innate immunity) and WT1-specific T cell-dependent antitumor effects (adaptive immunity).

Nonclinical pharmacology studies were performed to demonstrate that both the innate and adaptive immune system were activated by aAVC. Activation of innate immunity was demonstrated in a mouse lung metastatic cancer model, where NK cell depletion resulted in reduced antitumor effects. Activation of adaptive immunity was demonstrated in a second mouse model where mice were inoculated with AML tumor cells that either expressed WT1 or did not express WT1. In this model, aAVC (NIH3T3)-WT1 (ASP7517 surrogate) prolonged survival in the mice inoculated with the WT1-expressing tumor cells. In addition, studies of ASP7517 surrogate demonstrated increase of the production of CD8+ T cells secreting IFN γ by WT1 peptide stimulation. For additional information on ASP7517 please refer to Investigator's Brochure.

